2. SCHEDULE OF EVALUATIONS

	Visit 1	Visit 2	Visit 3	Visit 4	Visit 5	Visit 6	Visit 7
	Day	Day 0	Day 14	Day 28	Day 42	Day 56	Day 224
	(-14)	(±2)	(-2)	(-2)	(-2)	(-4)	(±7)
	Week -2		Week 2	Week 4	Week 6	Week 8	Week 32
Procedures	Screening	Baseline	Product Pick-Up	Treatment Follow-Up	Product Pick-Up	End of Treatme nt	Follow-up/ End of Study
ICF/HIPAA	X						
Demographics, Systemic and Ocular Medical History	X						
Collect date of Stage 1 NK initial diagnosis	X						
Pregnancy Test	X	X				X	
Record AEs	X	X	X	X	X	X	X
Concomitant Medications	X	X	X	X	X	X	X
IDEEL		X		X		X	X
EQ-5D-5L		X		X		X	X
BCDVA	X	X		X		X	X
External Ocular Examination	X	X		X		X	X
Slit Lamp Examination	X	X		X		X	X
Corneal Photography Without Fluorescein	X	X		X		X	X
TFBUT		X		X		X	X
FCS (NEI Scale)	X	X		X		X	X
Corneal Photography with Fluorescein	X	X		X		X	X
Corneal Sensitivity Testing	X	X		X		X	X
Schirmer Test (w/o Anesthesia)		X		X		X	X
IOP	X	X				X	X
Anterior Segment OCT (selected sites)		X				X	X
Confocal microscopy (selected sites)		X				X	X
Inclusion/Exclusion Criteria	X	X					
Assigned to Treatment		X					
Product Dispensation		X	X	X	X		
Collect Used/Unused Study Product			X	X	X	X	
AT Dispensation	X	-				X	
Dispense Daily Dosing Diary	X	X	X	X	X	X	
Evaluate Daily Dosing Diary			X	X	X	X	
Evaluate AT Use- in patient daily diary		X					X

2.1. BACKGROUND INFORMATION

Neurotrophic keratitis (NK), also known as neurotrophic keratopathy, is a rare degenerative corneal disease caused by an impairment of corneal nerve innervation leading to a decrease or absence in corneal sensation. The cornea is an avascular tissue that is provided with the richest innervation of all body tissues via the trigeminal nerve. Corneal hypoesthesia or anesthesia and decreased reflex tearing

resulting from impaired corneal innervation can lead to a corneal epitheliopathy with a subsequent breakdown of the corneal epithelium, leading to potential visual impairment. Abnormal corneal sensation and epithelial defects with a poor tendency for spontaneous healing are the primary clinical manifestations of NK, which increase the risk for corneal complications associated with vision loss such as a persistent epithelial defect (PED), ulceration, melting, perforation and infectious keratitis. Neurotrophic keratitis has been divided into three stages according to the Mackie classification scheme and treatment recommendations are based on the severity of the corneal involvement.^[1]

Based on the Mackie scale, Stage 1 NK is defined by the presence of an epithelial dystrophy or punctate keratopathy accompanied by corneal hypoesthesia. Stage 1 NK requires discontinuation of all topical medications and the administration of preservative-free artificial tears. While some Stage 1 NK patients may heal many do progress to Stage 2 NK. Based on the Mackie scale, Stage 2 NK is defined by the presence of a persistent epithelial defect (PED). The goal of treatment in Stage 2 is to avoid progression of the disease to a corneal ulcer. The same therapeutic approaches as in Stage 1 are used in patients with stage 2 often accompanied by the addition of patching or therapeutic contact lenses and the use of prophylactic antibiotics to prevent the risk of corneal infection. Based on the Mackie scale, Stage 3 NK is defined by the presence of a corneal ulcer, which may progress to corneal melting and perforation. When a corneal ulcer develops, therapy is aimed at promoting corneal healing and preventing corneal melting or perforation. Surgical procedures at this stage (tarsorrhaphy, flap procedures and amniotic membrane transplantation) can preserve or restore ocular integrity but at the expense of cosmetic appearance and visual function. As of today, the only FDA approved pharmacologic therapy for the treatment of NK is OXERVATE™ 0.002% (20 mcg/mL) cenegermin-bkbj ophthalmic solution, a recombinant human nerve growth factor (rhNGF). [4,5]

Nerve growth factor (NGF) is a polypeptide essential for the survival and growth of sympathetic and sensory neurons, and for differentiation of neurons in the central nervous system. It binds with at least two classes of receptors: high-affinity tropomyosin receptor kinase A (TrkA), a transmembrane tyrosine kinase, and low-affinity NGF receptor (LNGFR), also known as p75 neurotrophin receptor (p75NTR). [6, 7]

NGF and its receptors TrkA and p75 are expressed in the anterior segment of the eye (iris, ciliary body, lens, cornea, and conjunctiva), and NGF is released in the aqueous humor. Several pieces of experimental evidence suggest that NGF affects all tissues of the anterior ocular segments, playing a crucial role in the physiopathology of several anterior ocular segment diseases.^[8, 9]

OXERVATE[™] 0.002% (20 mcg/mL) cenegermin-bkbj ophthalmic solution is a recombinant human nerve growth factor approved by the FDA in August 2018 and it is indicated for the treatment of neurotrophic keratitis. Relevant pre-clinical, toxicological and clinical data are summarized below and can be found in the Package Insert (Appendix 3).^[4]

2.2. RELEVANT NON-CLINICAL PHARMACOLOGY

Both in vitro and in vivo data illustrate the biological activity of NGF in terms of neuronal growth and differentiation, as well as in prevention of apoptosis of retinal ganglion cells. Cultured corneal/limbal

cells of rabbit respond well to the proliferation stimulus induced by adding rhNGF or mNGF to the culture media. [10-12]

OXERVATE[™] 0.002% (20 mcg/mL) cenegermin-bkbj ophthalmic solution, a recombinant human nerve growth factor, is the first FDA-approved pharmacologic treatment that targets the root pathogenesis of neurotrophic keratitis.^[4]

Cenegermin-bkbj, the active ingredient of OXERVATE $^{\text{TM}}$ 0.002% (20 mcg/mL) cenegermin-bkbj ophthalmic solution, is structurally identical to the human nerve growth factor (NGF) protein made in ocular tissues.

NGF is an endogenous protein involved in the differentiation and maintenance of neurons, which acts through specific high-affinity (i.e., TrkA) and low-affinity (i.e., p75NTR) nerve growth factor receptors in the anterior segment of the eye to support corneal innervation and integrity. Endogenous NGF is believed to support corneal integrity through 3 mechanisms; corneal innervation, cell proliferation and tear secretion (shown in preclinical models).^[1, 2, 8, 13]

2.3. A SUMMARY OF CLINICAL DATA

The safety and efficacy of OXERVATE[™] 0.002% (20 mcg/mL) cenegermin-bkbj ophthalmic solution, was studied in a total of 151 patients with neurotrophic keratitis in two, eight-week, randomized controlled multi-center, double-masked studies. In the first study conducted in Europe NGF0212 (REPARO), patients were randomized into three different groups. One group received OXERVATE™ 0.002% (20 mcg/mL) cenegermin-bkbj ophthalmic solution, a second group received 10µg/mL cenegermin, and the third group received vehicle. [14] In the second study conducted in the US NGF0214, patients were randomized into two groups. One group was treated with OXERVATE[™] 0.002% (20 mcg/mL) cenegermin-bkbj ophthalmic solution the other group was treated with vehicle. [15] All eye drops in both studies were given six times daily at 2-hour intervals in the affected eye(s) for eight weeks. In the first study, only patients with the disease in one eye were enrolled, while in the second study, patients with the disease in both eyes were treated in both eyes (bilaterally), the worse eye was considered the study eye for efficacy evaluations. Complete corneal healing (defined as absence of staining of the corneal lesion and no persistent staining in the rest of the cornea at eight weeks) was demonstrated in 72 percent of patients treated with OXERVATE[™] 0.002% (20 mcg/mL) cenegerminbkbi ophthalmic solution compared to 33.3 percent of patients (p<0.001) treated with vehicle in the REPARO trial. For the US trial NGF0214, 65.2 percent of patients treated with OXERVATE[™] 0.002% (20 mcg/mL) cenegermin-bkbj ophthalmic solution compared to 16.7 percent of patients treated with vehicle had complete corneal healing at week 8.[14, 15]

The data from the two studies were enclosed into the biologics license application (BLA) and the FDA granted the approval for $OXERVATE^{TM}$ 0.002% (20 mcg/mL) cenegermin-bkbj ophthalmic solution for the treatment of all stages of NK.^[4]

2.4. STUDY RATIONALE

This clinical trial has been designed to demonstrate the efficacy and safety of OXERVATE[™] 0.002% (20 mcg/mL) cenegermin-bkbj ophthalmic solution given 6 times a day at 2-hour intervals for 8 weeks in patients with Stage 1 NK. Efficacy will be assessed as epithelial healing of Stage 1 NK as measured by corneal fluorescein staining. Further, the study will evaluate the preservation of effect measured by the percentage of treated patients who remain healed at the 32 week follow up.

2.4.1. Alternative treatments

The only FDA approved product for treatment of NK is OXERVATE[™] 0.002% (20 mcg/mL) cenegermin-bkbj ophthalmic solution. Alternative non-surgical treatment options may include therapeutic soft contact lenses, suture-less amniotic membrane, or tarsorrhaphy.

2.4.2. Description of the Study product

OXERVATE[™] 0.002% (20 mcg/mL) cenegermin-bkbj ophthalmic solution: in a multiple-dose vial.

3. OVERALL STUDY DESIGN AND INVESTIGATIONAL PLAN

3.1. STUDY OBJECTIVES

Primary Objective

The primary objective of this study is to evaluate the safety and efficacy of OXERVATETM 0.002% (20 mcg/mL) cenegermin-bkbj ophthalmic solution administered 6 times daily for 8 weeks on the ocular surface, visual function and quality of life in patients with Stage 1 NK.

Secondary Objective

The secondary objective is to evaluate patients who heal at week eight and remain healed (as defined in section 3.3) throughout the follow-up period. In addition, the study aims to evaluate the percentage of subjects that achieve an improvement in corneal sensitivity as measured by the Cochet-Bonnet aesthesiometer at 4 and 8 weeks, and by the last visit week 32.

Exploratory Objectives

The exploratory objectives are to evaluate change from baseline to weeks 4 & 8 in Schirmer I and the Tear Film Break-Up Time (TFBUT) change from baseline to weeks 4 & 8.

Additional Objectives (site specific)

Analysis to evaluate the change from baseline at week 8 and week 24 in confocal microscopy and anterior segment OCT.

3.2. STUDY ADMINISTRATIVE STRUCTURE

This study will be performed at approximately 5 study centers located in the United States. At each study center, the Principal Investigator (PI) will be responsible for ensuring that the investigation is conducted according to the signed Investigator agreement, the protocol, GCP guidelines, and local regulations.

The PI at each study center will be responsible for the management of the study, which will consist of maintaining the study file and the patient records, corresponding with the IRB/IEC, completing the case report forms (CRFs) and reporting SAEs (or other important AEs as specified in section 8.0) within 24 hours of initial awareness.

The PI is responsible for supervising any individual or party to whom the investigator delegates trial related duties and functions conducted at the trial site. If the investigator/institution retains the services of any individual or party to perform trial-related duties and functions, the investigator/institution should ensure this individual or party is qualified to perform those trial-related duties and functions and should implement procedures to ensure the integrity of the trial-related duties and functions performed and any data generated.

3.3. OVERALL STUDY DESIGN

This clinical study will be a multi-center, open label, prospective study of 8 weeks of treatment with 24 weeks of follow-up to evaluate the safety and efficacy of OXERVATE[™] 0.002% (20 mcg/mL) cenegermin-bkbj ophthalmic solution administered as one drop in the affected eye(s), 6 times per day at 2-hour intervals, for eight weeks in patients with Stage 1 Neurotrophic Keratitis (NK).

The study is divided into four phases as follows:

- 5. Screening Visit (Day -14): Procedures for inclusion will be performed at both Visit 1 (Screening) and Visit 2 (Baseline). Commercially available artificial tears (AT) provided by the sponsor will be permitted during the Screening period as needed up to four times a day.
- 6. Washout period (from day minus 14 to day 0): 14 days with no further treatment except commercially available preservative-free artificial tears provided by the sponsor. (Note: Xiidra™ and Restasis™ use is disallowed for 14 days prior to Visit 2.) Artificial tears (AT) provided by the sponsor will be permitted up to four times a day and will be tracked via daily diary during washout period.

7. **Treatment:**

- a. Treatment (weeks 1-8): eligible patients will start OXERVATE[™] 0.002% (20 mcg/mL) cenegermin-bkbj ophthalmic solution administered as one drop in the affected eye(s), 6 times per day at 2-hour intervals, for eight weeks. During the treatment period, only study product will be permitted for topical ocular treatment. *Commercially available preservative free artificial tears (AT) provided by Sponsor are not allowed during the treatment period.*
- 8. **Follow up (weeks 9-32):** For the 24 weeks post treatment:
 - a. For patients completely healed, no treatment is allowed except for commercially available AT provided by the Sponsor, administered at the physician's discretion. The use of artificial tears will be tracked via a daily dosing diary.
 - b. For patients not completely healed and who don't meet criteria for premature discontinuation, will also be followed up but any treatment is allowed at the discretion of the physician. All treatment will be tracked as concomitant medications.

Rescue Therapy: Commercially available preservative free artificial tears (AT) provided by Sponsor are not allowed during the treatment period. Per the investigator's discretion if the patient requires rescue therapy during the 8-week treatment period then they can receive artificial tears provided by the sponsor for up to four times per day. The frequency of rescue therapy must be documented in the patient's diary.

The study will be a total of 34 weeks in duration: a screening period of 2 weeks, followed by 8 weeks of treatment and a 24-week follow-up period. At the end of the screening period (at Visit 2), patients meeting the entry criteria for this study will be assigned to treatment with OXERVATE[™] 0.002% (20

mcg/mL) cenegermin-bkbj ophthalmic solution which will be known as Study Product beginning the morning following Visit 2.

Following the completion of the treatment period, patients will be followed up for an additional 24 weeks (for patients healed and non-healed [and not meeting d/c criteria] at Week 8) and will be evaluated at the end of the follow-up period. At the investigator's discretion, the subject may be seen for an Unscheduled Visit to evaluate for safety. Patients who prematurely discontinue for whatever reason will not be followed post discontinuation and should have Visit 6 assessments completed.

At Visit 1, eligible patients will be instructed to discontinue all topical ophthalmic medications and will only be allowed to use commercially available preservative free tears provided by the sponsor to be used up to four times per day during the screening period. At the conclusion of the Baseline Visit (Visit 2) eligible patients will be dispensed a 2-week supply of Study Product from the onsite freezer in a sealed bag and will be instructed to self-administer the Study Product one drop six times a day starting on the day after Day 0/ Visit 2 through Week 8 of the controlled treatment period according to the dosing schedule shown in Table 1 (Dosing Schedule).

Table 1 Dosing Schedule

TREATMENT	TREATMENT DOSING SCHEDULE*
OXERVATE™ 0.002% (20 mcg/mL) cenegermin-bkbj ophthalmic solution	Morning (8 AM)
	Mid-morning (10 AM)
	Noon (12 PM)
	Early afternoon (2 PM)
	Mid afternoon (4 PM)
	Late afternoon (6 PM)

^{*} The above is an example. The timing of instillation can be adjusted if a patient's awakening and/or bedtime differs throughout the 8 weeks. The patient should try and keep the daily dosing schedule as consistent as possible by trying to schedule sleep and wake times. A daily dosing diary will be maintained by the subject to track compliance for each dose of study product.

A two week supply of study product will additionally be dispensed to the patients during the treatment period at Visits 3, 4 and 5/Weeks 2, 4 and 6.

Starting from Visit 2, only the study product will be allowed. Preservative free AT provided by the sponsor *will not* be used during the study product treatment period. After the 8 weeks of Study Product treatment, and during the follow up period, AT should be used only if strictly needed. The use of AT will be tracked in the daily dosing diary.

At Visit 6 (End of Treatment), patients will be assessed for corneal healing.

Completely healed patients at week 8 are defined by SPK as Grade ≤1 in the central qualifying zone via FCS (per NEI scale) and no persistent staining in the non-qualifying zones (excluding the superior zone) defined as the absence of pathological staining via corneal photography. Patients who are completely healed at Week 8 will be followed for an additional 24 weeks during the follow-up period. During the 24-week follow-up period (Weeks 9-32) the patients will be followed without any Study Product, however, preservative-free AT (provided by the study sponsor) may be used documented on the daily diary. If warranted for patient safety, the Investigator may elect to see the subject at an Unscheduled Visit(s) to evaluate the patient.

Patients who are not completely healed at week 8 are defined by SPK as Grade 2 via FCS in the central qualifying zone AND who do not meet the criteria for premature discontinuation, will also be followed for an additional 24 weeks during the follow-up period. During the 24 week follow-up period (Weeks 9-32) the patients will be followed may be treated at the physician's discretion (retreatment with OXERVATE™ 0.002% (20 mcg/mL) cenegermin-bkbj ophthalmic solution is not permitted). Any concomitant treatment must be documented on concomitant medication log. If warranted for patient safety, the Investigator may elect to see the subject at an Unscheduled Visit(s) to evaluate the patient.

Patients who meet the definition of Deterioration or No Improvement in the study eye at week 8 and during the follow up period, will be discontinued from the study and treated as appropriate at the discretion of the investigator.

Deterioration or No Improvement is defined by any of the following:

- In the Study Eye, the FCS is unchanged (Grade=3) from baseline in the qualifying NEI zone.
- At the PIs discretion, in the study eye there is a progression from baseline in the non-qualifying zones
- decrease in BCDVA by >10 ETDRS letters from baseline.
- progression in staining to a PED or corneal melting or perforation
- onset of infection
- Require an ocular surgical procedure, including the need for a corneal transplant.

Note: If there is a deterioration in the non-study eye, the Investigator may discontinue treatment in that eye and initiate alternative treatment at their discretion in the non-study eye, but continue following the study eye per protocol.

[figure not shown]
All patients will attend the following clinic visits in the following sequence:

- Screening (Visit 1/Day -14)
- Baseline and First Study Product Pick-Up (Visit 2/Day 0)
- Product Pick-Up (Visit 3/Week 2)
- Treatment Assessment and Study Product Pick-Up (Visit 4/Week 4)
- Product Pick-Up (Visit 5/Week 6)
- End of 8-week Treatment (Visit 6/Week 8)
- Follow-Up and Final Study Visit (Visit 7/Week 32).

The trial structure for subjects is shown in **Figure 1**

Figure 1 Study Schematic

Any subject who meets the definition of experiencing a deterioration in the study eye, will be discontinued from the study, and followed per the Investigator's discretion.

If there is a deterioration in the non-study eye, the Investigator may discontinue treatment in that eye and initiate alternative treatment at their discretion in the non-study eye, but continue following the study eye per protocol.

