- 2. Washout period (from day minus 14 to day 0): 14 days with no further treatment except commercially available preservative-free artificial tears provided by the sponsor (Note: Xiidra[™] and Restasis[™] use is disallowed for 14 days prior to Visit 2.) Artificial tears (AT) provided by the sponsor will be permitted up to four times a day and will be tracked via daily diary during washout period.

3. **Treatment:**

- a. Treatment (weeks 1-8): eligible patients will start OXERVATETM 0.002% (20 mcg/mL) cenegermin-bkbj ophthalmic solution administered as one drop in the affected eye(s), 6 times per day at 2-hour intervals, for eight weeks. During the treatment period, only study product will be permitted for topical ocular treatment.

 Commercially available preservative free artificial tears (AT) provided by Sponsor are not allowed during the treatment period except as rescue therapy.
- 4. Follow up (weeks 9-32): For the 24 weeks post treatment:
 - a. For patients completely healed, no treatment is allowed except for commercially available AT provided by the Sponsor, administration frequency is at the physician's discretion during follow-up based on patients need for

Study Design and Methodology

- lubrication. The use of artificial tears will be tracked via a daily dosing diary.
- b. For patients not completely healed and who don't meet criteria for premature discontinuation, will also be followed up but any topical treatment is allowed at the discretion of the physician. All treatments will be tracked as concomitant medications. No surgical procedures are permitted during the follow-up (i.e. sutured Amniotic Membrane Transfer (AMT), sutured tarsorrhaphy). Permitted items include topical medications and suture less AMT.

The study will be a total of 34 weeks in duration: a screening period of 2 weeks, followed by 8 weeks of treatment and a 24-week follow-up period. At the end of the screening period (at Visit 2), patients meeting the entry criteria for this study will be assigned to treatment with OXERVATE[™] 0.002% (20 mcg/mL) cenegermin-bkbj ophthalmic solution which will be known as Study Product beginning the morning following Visit 2.

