Completely healed patients at week 8 are defined by SPK as Grade ≤1 in the central qualifying zone via FCS (per NEI scale) and no persistent staining in the non-qualifying zones (excluding the superior zone) defined as the absence of pathological staining via corneal photography. Patients who are completely healed at Week 8 will be followed for an additional 24 weeks during the follow-up period. During the 24-week follow-up period (Weeks 9-32) the patients will be followed without any Study Product, however, preservative-free AT (provided by the study sponsor) may be used and documented on the daily diary. If warranted for patient safety, the Investigator may elect to see the subject at an Unscheduled Visit(s) to evaluate the patient.

Patients who are not completely healed at week 8 defined by SPK as Grade 2 via FCS in the central qualifying zone AND who do not meet the criteria for premature discontinuation, will also be followed for an additional 24 weeks during the follow-up period. During the 24-week follow-up period (Weeks 9-32) the patients will be followed and may be treated at the physician's discretion (retreatment

with OXERVATE[™] 0.002% (20 mcg/mL) cenegerminbkbj ophthalmic solution is not permitted). Any concomitant treatment must be documented on concomitant medication log. If warranted for patient safety, the Investigator may elect to see the subject at an Unscheduled Visit(s) to evaluate the patient.

Patients who meet the definition of Deterioration or No Improvement in the study eye at week 8 and during the follow up period, will be discontinued from the study and treated as appropriate at the discretion of the investigator. Deterioration or No Improvement is defined by any of the following:

[figure not shown]
- In the Study Eye, the FCS is unchanged (Grade=3) from baseline in the qualifying NEI zone.
- At the PIs discretion in the study eye if any of the non-qualifying zones progress from baseline.
- decrease in BCDVA by >10 ETDRS letters from baseline.
- progression in staining to a lesion/PED or corneal melting or perforation.
- onset of infection (viral, fungal, bacterial)
- Require an ocular surgical procedure, including the need for a corneal transplant.

Note: If there is a deterioration in the non-study eye, the Investigator may discontinue treatment in that eye and initiate alternative treatment at their discretion in the non-study eye but continue following the study eye per protocol.

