5.3.1. Prior and concomitant medications

As a general rule, no ophthalmic medication other than Study Product and concomitant Study Product (Systane[®] -artificial tears provided by Sponsor) will be given to the patient from the screening day until all the final study evaluations have been completed. Systane[®], provided by the Sponsor, may be used *during screening and the follow up only*.

All medications (including over-the-counter drugs, systemic medications, herbal products, vitamins, and antacids) should be documented at screening and also taken within 14 days of study treatment Visit 2 and throughout the study will be clearly documented on the Concomitant Medications eCRF page.

Medication entries should be specific to product name (if a combination drug product) and spelled correctly. The dose, unit, frequency, route of administration, start date, discontinuation date, and indication should also be recorded. For medications administered only one time, the frequency column may reflect "once."

D Dompo	
Table 3 Medications and Procedures	Minimum Washout Period Prior to Treatment (Visit 2)
Have had incisional ocular surface surgery (e.g., LASIK, refractive, pterygium removal).	90 days
Ocular surgery (including eyelid surgery or cataract surgery)	90 days
Botox (botulinum toxin) injections in the study eye.	60 days
Any Investigational Product for NK	60 days
Any Investigational Product applied to the ocular surface if per the investigators discretion the investigational product does not have residual effects on the ocular surface that can confound the data	14 days
Topical ocular or systemic antibiotics for the treatment of an ocular condition	14 days
Topical cyclosporine (all doses and formulations)	14 days
Lifitegrast	14 days
Glaucoma topical medications (Use of Diamox orally during the study is acceptable)-Investigator should ensure stable IOP before/by Visit 2	14 days
Topical ocular corticosteroids, ocular non-steroidal anti- inflammatory drugs (NSAIDs), and topical dermatologic corticosteroids on the face within 14 days prior to Visit 2 and during study participation	14 days
Topical ocular antihistamine and/or mast cell stabilizers within 14 days prior to Visit 2. Have used topical ocular vasoconstrictors for the purpose of eye whitening within 14 days prior to Visit 2 (phenylephrine used to dilate the eyes is allowed).	14 days

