1.3.2.2 Rescue Therapy

Commercially available preservative free artificial tears (AT) provided by Sponsor are not allowed during the treatment period. Per the investigators discretion if the patient requires rescue therapy during the 8-week treatment period then they can receive artificial tears provided by the sponsor up to four times per day. The frequency of rescue therapy must be documented in the patient's diary.

During the 24 weeks post treatment, for patients completely healed, no treatment is allowed except for commercially available AT provided by the Sponsor, administered at the physician's discretion. The use of AT will be tracked via a daily dosing diary. Patients not completely healed and who don't meet criteria for premature discontinuation will also be followed up but any treatment is allowed at the discretion of the physician, with the exception of additional Oxervate[™].

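### The epithelial-healing durability rate is scored on the central zone, but follow-up therapy depends on complete healing, so some patients given other therapy in Weeks 9-32 can count as having remained healed

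*Protocol*

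**What the plan says.** **Who may be treated in follow-up.** Protocol 3.3 makes complete healing a two-part condition: central Grade 1 or less, and no pathological staining in the non-qualifying zones other than the superior one. Item 8a says: "For patients completely healed, no treatment is allowed except for commercially available AT provided by the Sponsor". Item 8b says that patients not completely healed, and not meeting discontinuation criteria, "will also be followed up but any treatment is allowed at the discretion of the physician". The synopsis narrows this to topical treatment without surgery: "Permitted items include topical medications and suture less AMT". SAP 1.3.2.2 repeats the rule: "any treatment is allowed at the discretion of the physician, with the exception of additional Oxervate". None of these three places gives a staining grade.

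**The Grade 2 sentence.** Later in Protocol 3.3, and in the synopsis, the group that is not completely healed is described by the central zone alone: "Patients who are not completely healed at week 8 are defined by SPK as Grade 2 via FCS in the central qualifying zone".

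**How durability is scored.** SAP 5.1 defines epithelial healing as Grade 0 or 1 in the central zone. SAP 5.2 applies that definition at Week 32, among Week 8 epithelial healers and in the Full Treated Set (FTS). Protocol 7.1.1, endpoint 2, also uses the epithelial definition. A separate durability rate is based on complete healing.

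**How other therapy is handled.** The only rule that turns therapy into failure is a sensitivity analysis in SAP 5.1. It covers rescue use before Week 8.

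**The concern.** Two definitions of healing are in use. The stricter one decides who may be treated, and the looser one decides who counts as a durable success. A patient who meets the looser definition but not the stricter one can be treated for 24 weeks and still be scored as having kept the product's benefit. Protocol 2.4 describes the aim of the follow-up as preservation of effect. With a single arm, nothing else in the design separates a lasting effect of eight weeks of cenegermin from the effect of whatever was given afterwards. At stake is the interpretation of one of the two durability rates.

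**Working it through.** **Step 1. The plan's own figure.** Protocol 9.1 gives lower 95% limits of 40% and 54% for N = 35 at healing rates of 58% and 72%. The exact (Clopper-Pearson) lower limit, the 2.5% quantile of Beta(x, n - x + 1) with x = n × p, gives 40.2% and 54.3%. The stated precision reproduces, and this point does not alter it.

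**Step 2. Retained patients at Week 8, by staining.**

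| Central zone | Temporal, nasal, inferior zones | Follow-up rule | Week 8 epithelial healer? |
|---|---|---|---|
| Grade 0-1 | Clear | Tears only | Yes |
| Grade 0-1 | Residual, not progressing | Any permitted therapy, reading not completely healed as the complement | Yes |
| Grade 2 | Any, not progressing | Any permitted therapy | No |
| Grade 3 (unchanged) | Any | Discontinued | No |

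Only the second row combines access to other therapy with eligibility for the epithelial durability count. Discontinuation does not empty it: Protocol 3.3 and 6.2 act on progression or an increase in a non-qualifying zone, not on staining that is stable or reduced. Protocol 4.1 requires central Grade 3 at entry and sets no limit on staining elsewhere.

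**Step 3. Effect of one patient.** The documents give no frequency for the second row.

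- Healers at the planning rate: 0.72 × 35 = 25.2, about 25.
- Healers at 65.2%: 0.652 × 35 = 22.8, about 23. This is the complete-healing rate from the earlier US trial (Protocol 2.3), used here only as an assumed lower value.
- Change per reclassified patient: 1/25 = 4.0 points or 1/23 = 4.3 points among healers; 1/35 = 2.9 points in the FTS.

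**Step 4. Scale against the interval.** Assume that 20 of 25 healers are healed at Week 32 and that one is reclassified.

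| | Plain rate (exact 95% CI) | One reclassified (exact 95% CI) |
|---|---|---|
| Among healers | 20/25 = 80.0% (59.3 to 93.2) | 19/25 = 76.0% (54.9 to 90.6) |
| FTS | 20/35 = 57.1% (39.4 to 73.7) | 19/35 = 54.3% (36.6 to 71.2) |

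One patient matters little beside these intervals. If g patients were reclassified, the change would be g/25 or g/35: zero for g = 0; 12.0 and 8.6 points for g = 3; 20.0 and 14.3 points for g = 5. These values of g are assumptions.

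**The case against.** A reader might infer from the Grade 2 sentence that the healed-centre, stained-periphery patient has no follow-up treatment rule at all. The documents do not support that. Item 8b, the synopsis and SAP 1.3.2.2 give the discretionary rule to everyone not completely healed, with no grade attached, and SAP 5.2 has complete healing recorded by the investigator and summarised as yes or no. Read together, these supply a workable complement. The general rule in Protocol 5.3.1, that no ophthalmic medication beyond study product and sponsor tears "will be given to the patient from the screening day until all the final study evaluations have been completed", cannot override them. Taken literally it would also bar the therapy that the protocol expressly allows at central Grade 2. So the wording is a drafting slip, and correcting it alone would only confirm that these patients may be treated.

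A reader might also take the 4 points as an estimate of bias. It is the arithmetic of counting a treated patient as not maintained. Nothing in the documents shows that the central zone would have relapsed without therapy given for peripheral staining.

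It is also fair to say that the consequence is partly contained. The analyses are exploratory (SAP 2.10), no hypothesis is tested, follow-up medications are tabulated (SAP 4.2), and staining and medications are listed by subject, so the link could be rebuilt by hand. These points limit the importance of the issue. They do not supply a prespecified account of follow-up therapy in the epithelial durability rate.

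**Conclusion.** The mismatch is real and its reach is limited. On the natural reading of the follow-up rules, a Week 8 epithelial healer with residual peripheral staining may receive other therapy in Weeks 9-32 and count as durably healed, and the SAP does not address this. If such patients were in practice held to artificial tears, the issue would not arise.

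The size is 4.0 to 4.3 points among healers, or 2.9 points in an FTS of 35, for each patient reclassified. The total depends on a count that the documents do not give.

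The Week 8 primary estimate is unaffected, because the therapy in question starts afterwards. The complete-healing durability rate is largely protected: its Week 8 successes are limited to tears, and the patients at issue are outside its healer subset and are non-successes in its FTS version. It is also the version closest to the secondary objective, which points to Protocol 3.3 for its meaning of healed. This is a low-cost improvement and not a defect that threatens the study's main result.

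**What to change.** **Main change, SAP 5.2, with no protocol amendment needed.** Keep the plain epithelial-healing durability rate. Add one sensitivity row that counts as not maintained any Week 8 epithelial healer who started ocular therapy other than artificial tears, including sutureless amniotic membrane, for NK or ocular-surface disease after the Week 8 assessment. Identify the therapy from the start date and indication already collected (SAP 1.3.2.1). Leave artificial tears out of the rule, because they are allowed in follow-up. Limit the row to study-eye therapy if the medication log records the treated eye. That field is not among those listed, so check it first.

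**Secondary change.** At the next protocol amendment, align the Grade 2 sentence in Protocol 3.3 and the synopsis with the complement: any retained patient who fails either part of complete healing. This is editorial and does not justify an amendment of its own.

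**Cost.** One extra table row, and some case-by-case judgement on indication. The row may be lower than the plain rate by the per-patient amounts above; the plain rate itself does not change.
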